- c. A standard urine drug screen will be performed (Appendix 3). Participants who test positive will be assessed for eligibility for study participation by the Investigator after discussion with the Medical Monitor.
- d. TB screening includes any of the following: 1) history of untreated or inadequately treated latent TB (see Exclusion Criterion 15 for exceptions); 2) a positive diagnostic TB test within 1 month of enrollment (defined as a positive QuantiFERON test or 2 successive indeterminate QuantiFERON tests; or a tuberculin skin test reaction ≥ 10 mm [≥ 5 mm in participants receiving the equivalent of > 15 mg/day prednisone], if a QuantiFERON test is unavailable).
- e. Chest X-ray to be performed if not done in previous 6 months.
- f. Includes HIV, HBV, and HCV testing.
- g. Stool culture for bacterial pathogens, ova, and parasites, and for *Clostridium difficile* test.

- h. Study drug should be administered after completion of all initial assessments on the day of visit. On Day 1, the participant will remain in clinic for 6 hours of cardiac monitoring after dosing.
 - i. Concomitant medications include over-the-counter or prescription medicines, blood products, vaccines, vitamins, holistic products, and radiotherapy.
 - j. ECGs to be obtained after an at least 5-minute supine resting period. At Visit 2, 12-lead ECGs will be collected predose and at 1, 2, 4, and 6 hours (± 10 minutes) postdose. The predose ECG at Visit 2 should be performed and assessed prior to randomization. When study drug is to be administered at the clinic, ECG will be obtained predose.
 - k. At Visit 2, continuous Holter ECG monitoring will be performed for at least 1 hour predose and at least 24 hours postdose.
 - l. Vital signs (including HR and BP) will be collected in the sitting position prior to the ECG assessment and before any simultaneously scheduled blood collections. At Visit 2, vital signs will be collected predose and at 1, 2, 4, and 6 (± 10 minutes) hours postdose.
 - m. At the 2-Week Follow-Up visit, if the absolute peripheral lymphocyte count is not within normal limits, participants should return for CBC with differential according to local standard of care (captured as subsequent Follow-Up visit or unscheduled visit).
 - n. Blood samples will be collected as detailed in the Laboratory Manual. [REDACTED]

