2.2.2.3 Pharmacodynamics

There was a dose-related mean reduction in absolute lymphocyte counts (ALC), as measured by percent change from baseline, following all single and multiple oral doses of VTX002 compared with placebo. Maximum mean percent change from baseline across all treatments occurred at

approximately 3 to 8 hours after dosing. Based on maximum mean percent change from baseline following a single oral dose of VTX002, the greatest reduction in ALC (65.4%) was associated with the largest plasma VTX002 C_{max} value attained following the 40 mg VTX002 dose. Similarly, the largest reductions in ALC were associated with the highest plasma VTX002 trough concentration values following multiple oral VTX002 QD doses. At steady state, the mean percent reductions in ALC were similar for the 35 and 45 mg QD VTX002 doses (62% and 65%, respectively), as were the mean maximum observed reductions in ALC for the 35 and 45 mg QD VTX002 doses (75% and 74%, respectively).

2.2.2.4 *Cardiodynamics*

Assessment of QT intervals through linear regression of corrected QT using Fridericia's formula (QTcF) versus RR indicated adequacy of QTcF. QTcF versus time profiles were similar across all VTX002 doses, with slightly greater mean values noted following 25 mg VTX002 (single ascending dose [SAD]) and 10 mg VTX002 (multiple ascending dose [MAD]). All participants in the SAD and MAD cohorts exhibited QTcF intervals ≤ 450 msec, and there were no participants with change from baseline values > 30 msec.

2.2.2.5 *Heart Rate Analysis*

In the SAD cohorts, there was a dose-related decrease in HR after dosing with VTX002 compared with placebo, with the maximum HR decrease from baseline (defined as the interval time between -1 hour to dose) occurring during Hour 1 (defined as the interval time between 1 and 2 hours postdose) with rapid increase after the nadir, returning to baseline by Hour 3 (defined as the interval time between 3 and 4 hours postdose). The maximum decrease from baseline of -21.2 beats per minute (bpm) (-30.80%) occurred during Day 1, Hour 1 (defined as the interval time between 1 and 2 hours postdose) among participants in the 40 mg VTX002 cohort.

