7.3 Safety Endpoints

- Incidence and severity of adverse events (AEs)
- Incidence and severity of laboratory abnormalities, and change from baseline in laboratory values (e.g., hematology and serum chemistry)
- Incidence of clinically significant vital sign abnormalities and changes from baseline

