9.6 Windowing Conventions

All scheduled study visits are defined relative to Study Day 1, the date of first Induction Treatment Period dose.

Scheduled visit windows for the Induction Treatment Period are defined in Protocol VTX002-201 Section 1.2 Table 1. Scheduled visit windows for the LTE are defined in Protocol VTX002-201 Section 1.2 Table 2. Scheduled visit windows for the OLE are defined in the Protocol VT002-201 Section 1.2 Tables 3, 4, 5, and 6.

A windowing convention will be used to determine the analysis visit value for a given measurement and will be applicable for all by-visit summaries and analyses for efficacy and safety data. Refer to [Table 3](#) for specific Induction Treatment Period visit windows.

Windowing will be applied prior to any missing data calculations. The last non-missing measurement taken prior to Day 1 (including unscheduled assessments) will be labeled as Baseline. Unless stated otherwise, data from scheduled, unscheduled, and early termination site visits will be eligible for allocation to an analysis visit. Follow-up visit data is handled as-is.

Table 3. Analysis Visit Windows

	Visit Label	Study Week	Ideal Study Day (Study Day)	Protocol Visit Window (Study Day)	Analysis Visit Window (Study Day)
Non-Efficacy, Physician's Global Assessment (PGA), IBDQ ^a	Visit 1/Baseline	n/a	-14	[-28, -1]	≤1
	Visit 2	0	1	[1]	[1, 4]
	Visit 3	1	8	[8, 10]	[5, 18]
	Visit 4	4	29	[26, 32]	[19, 42]
	Visit 5	8	57	[54, 60]	[43, 63]
	Visit 6	10	71	[68, 74]	[64, 81]
	Visit 7	13	92	[89, 95]	[82, 102]
Endoscopy and Colonic Biopsy ^b	Visit 1/Baseline	n/a	-14	[-28, -1]	≤1
	Visit 7	13	92	[89, 95]	[76, 108]
SF and RB calculated from eDiary entries ^{b, c}	see footnote	see footnote	see footnote	see footnote	see footnote
Early Term /Unscheduled ^d	see footnote	see footnote	see footnote	see footnote	see footnote
1-Week Follow-up ^d	1-Week Follow-up	n/a	X+7	n/a	n/a
2-Week Follow-up ^d	2-Week Follow-up	n/a	X+14	n/a	n/a

^a Analysis visit windows and Ideal Study Days are intended to map, to Study Visits, all by-visit data collected during the Induction Treatment Period.

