data from ET and Unscheduled visits not associated with Visit 7 will be listed only. 1-Week and 2-Week Follow-up data is not windowed and presented according to nominal visit label in tables.

For composite scores such as MMS, if one or more components is missing from an analysis visit window the composite score is missing. If one or more results for a variable are assigned to the same analysis visit, the result with the date closest to the protocol Ideal Study Day will be used in the analysis, except for rectal bleeding and stool frequency component subscores used in the determination of Symptomatic Remission, Symptomatic Response, MMS, or total MCS. In this case, 7-day look-back windows anchored to either an endoscopy or a site visit are used to determine the component subscores.

If two measurements in the same analysis visit window are equidistant from the protocol scheduled study day, the earliest measurement will be used in the analysis. If multiple assessments are available on the same day, then the average of the assessment will be used in the analysis, except for laboratory data where the assessment at the earliest time of the same day will be used. Central laboratory assessments will be used in both summaries and listings, while local laboratory assessments will only be separately listed. Local laboratory data may be used by investigators to help inform participant safety decisions and adverse event reporting.

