17.3 Vital Signs

Similar to laboratory data analysis, three sets of vital signs summaries will be prepared: for Induction Treatment Period, LTE and OLE Treatment Periods. Safety Set will be used for induction treatment summaries and Safety-ET Set for LTE/OLE summaries.

Vital signs include data on pulse rate (bpm), systolic/diastolic blood pressure (mmHg), respiratory rate (breaths/min), temperature ($^{\circ}\text{C}$), weight (kg) and height (cm). Descriptive statistics will be provided for observed values, change from baseline, and percent change from baseline to post-baseline time points for every parameter. Visit windowing will be used to associate vital sign data with study visits – see [Section 9.6 Table 3](#).

A listing of vital signs data will be presented.

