17.5.1 Twelve-Lead ECG

ECG data will be presented by treatment group for each study period (Induction, LTE, OLE) and overall.

The 12-lead ECG data will include heart rate (bpm), RR (msec), PR (msec), QRS (msec), QT (msec) and QTcF (msec) intervals. Absolute values and changes from baseline to post-baseline time points will be summarized using descriptive statistics for quantitative variables. Shift tables from baseline ('Normal', 'Abnormal, not clinically significant' and 'Abnormal, clinically significant') to each visit will be provided. ECG data will be read locally as well as centrally. Only central ECG data will be used for summaries, all available ECG data from local and central readers will be listed. Actual results will not be reconciled. In case of several assessment within timepoint, the earlier assessment will be used for the analysis.

The following incidences will be summarized by number and percentage at every post-baseline visit:

- QT interval
 - ≥ 500 msec
 - Change from baseline $> +30$ msec
 - Change from baseline $> +60$ msec
- QTcF interval
 - ≥ 450 msec (male) or ≥ 470 msec (female)
 - Change from baseline $> +30$ msec
 - Change from baseline $> +60$ msec
- PR interval
 - PR > 200 msec
 - PR > 230 msec
- HR
 - < 40 beats/min (bpm)

- < 50 bpm
- > 110
- Change from baseline < -10 bpm
- AV Block
 - First-degree AV Block
 - Second-degree AV Block Type 1
 - Second-degree AV Block Type 2
 - Third-degree AV Block

The denominator will be the number of participants in treatment group with non-missing results at the specified visit.

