17.5.2 Holter ECG monitoring

On Day 1 of Induction Treatment Period and OLE Day 1 continuous Holter ECG monitoring will be performed for at least 1 hour predose and at least 24 hours postdose.

Overall interpretation ('Normal', 'Abnormal', 'Not Evaluable') will be summarized by number and percentage. Denominator will be the number of participants available at specified visit in treatment group.

Parameters of interest will be listed.

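### Read literally, SAP 9.6 and 17.3 average the serial Day 1 vital signs into one Visit 2 value, which dilutes a transient heart-rate fall; the promised vital-sign abnormality incidence is also not planned

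*SAP*

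**What the plan says.** The windowing convention in SAP 9.6 "will be applicable for all by-visit summaries and analyses for efficacy and safety data". Within it, the rule for several results on one day is "If multiple assessments are available on the same day, then the average of the assessment will be used in the analysis". The exception written into that sentence is for laboratory data, where the earliest result of the day is taken.

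SAP 17.3 applies this to vital signs: "Visit windowing will be used to associate vital sign data with study visits". It promises descriptive statistics for observed values and changes to post-baseline *time points*, a term it does not define, and a listing. It plans no table of abnormal values. Yet SAP 7.3 names as a safety endpoint "Incidence of clinically significant vital sign abnormalities and changes from baseline", and Protocol 9.4.3 says the incidence of treatment-emergent abnormal vital signs will be summarized. SAP 18 does not record a departure from this.

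The readings in question are set out in the Protocol 1.2, Table 1 footnotes: "At Visit 2, vital signs will be collected predose and at 1, 2, 4, and 6" hours after the dose. The Table 3 footnotes set the same times for OLE Day 1.

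The 12-lead ECG, taken at the same hours, has its own rule in SAP 17.5.1: "In case of several assessment within timepoint, the earlier assessment will be used for the analysis". Its heart-rate, PR and AV-block incidences are tabulated per post-baseline visit. For Holter, SAP 17.5.2 tabulates the overall interpretation; beyond that, "Parameters of interest will be listed".

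**The concern.** Serial readings are taken after the first dose because the effect is brief. Protocol 2.2.2.5 describes a Phase 1 heart-rate fall that was greatest 1 to 2 h after a single dose and had gone by 3 to 4 h. An average over predose, nadir and recovered readings measures something else, and it shrinks any short-lived fall by a factor that depends only on how many readings catch it.

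Protocol 2.3 lists decreased heart rate and AV conduction first among the potential risks and ties the 6-hour clinic stay to it. The vital-sign table is where a reader would look for the by-arm size of the effect. As specified, that table would give one diluted Day 1 figure per arm, with no count of participants below any threshold.

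**Working it through.** The plan states no figure for this point, so there is none to reproduce. The check has two parts: what the text does to the Day 1 series, and how much dilution follows.

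**What the text does**

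- SAP 9.6 seeks one analysis value per visit and averages same-day results. SAP 17.3 refers to it and adds no within-day rule.
- SAP 9.8 defines change from baseline as the value at a visit minus baseline. This favours reading the undefined *time points* of 17.3 as visits, though it does not settle the matter.
- Whether the predose reading enters the average is unclear. SAP 9.5 uses date and time, so a predose Day 1 reading can be baseline, and Protocol 6.5 treats it as such. SAP 9.6 labels as baseline the last value before Day 1. In SAP Table 3 the Baseline window (Day 1 or earlier) and the Visit 2 window (Days 1 to 4) overlap on Day 1. Both denominators are therefore shown.

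**Dilution**

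Input: Protocol 2.2.2.5, 40 mg single-dose cohort: "The maximum decrease from baseline of -21.2 beats per minute (bpm) (-30.80%) occurred during Day 1, Hour 1", with return to baseline by Hour 3. Assumptions: change is 0 at predose, 4 h and 6 h; the 1 h reading shows the full fall; the 2 h reading lies between 0 and the full fall. Mean change = (sum of changes) / (number of readings).

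| 1 h and 2 h change (bpm) | Mean of 5 readings | Mean of 4 postdose readings |
|---|---|---|
| -21.2 and 0 | -21.2/5 = -4.24 | -21.2/4 = -5.30 |
| -21.2 and -10.6 | -31.8/5 = -6.36 | -31.8/4 = -7.95 |
| -21.2 and -21.2 | -42.4/5 = -8.48 | -42.4/4 = -10.60 |

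The average keeps between 1/5 (20%) and 2/4 (50%) of the nadir. The quoted percentage implies a baseline of roughly 21.2/0.308 = 68.8 bpm and a nadir of 68.8 - 21.2 = 47.6 bpm. The averaged heart rate would read between 68.8 - 4.2 = 64.6 and 68.8 - 10.6 = 58.2 bpm.

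The documents give no effect for the 3 mg Day 1 dose, so a range of assumed nadirs is shown:

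| Assumed nadir (bpm) | Mean of 5 (x 1/5 to 2/5) | Mean of 4 (x 1/4 to 1/2) |
|---|---|---|
| -5 | -1.0 to -2.0 | -1.25 to -2.5 |
| -10 | -2.0 to -4.0 | -2.5 to -5.0 |
| -15 | -3.0 to -6.0 | -3.75 to -7.5 |

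**Other outputs that carry first-dose heart rate**

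- ECG (SAP 17.5.1): not averaged, with rows for heart rate below 40 and below 50 bpm, change below -10 bpm, PR and AV block. The rows are per visit, and the text does not say which of the Day 1 traces counts. If *timepoint* means the visit, the earlier trace could be the predose one. If it means the hour, the trace behind the Visit 2 count is undefined.
- Holter (SAP 17.5.2): a by-arm count of overall interpretation, but no by-arm heart-rate summary.
- Targeted medical events (SAP 17.1.3): bradycardia and AV conduction delay are tabulated. They depend on an adverse event having been reported, which under Protocol Appendix 4 requires the investigator to judge the abnormality clinically significant.

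**The case against.** The strongest reply is that this is a wording gap in one table. The *time points* of SAP 17.3 may well mean nominal hours. The detailed shells are in the Mock TFLs file (SAP 19 and 20), which is not part of these documents and may already have hourly rows. The Phase 1 figure is from an untitrated 40 mg dose, whereas Day 1 here is 3 mg. After titration in Phase 1, the first target-dose changes were only -3.5 and -3.3 bpm (Protocol 2.2.2.6 follows; the figures are in 2.2.2.5). These points stand in part: the text is ambiguous, and the size of the effect in this trial is unknown. They do not remove the stated averaging rule or supply an hourly one.

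A reader might infer more than the documents support:

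- *That every same-day non-laboratory result is averaged.* ECG has its own rule, and the eDiary stool-frequency and rectal-bleeding subscores use look-back windows.
- *That the ECG table keeps only one early trace.* The SAP does not say so; it leaves the choice of trace open.
- *That the averaged falls would miss the SAP's -10 bpm cut-off.* That cut-off applies to ECG heart rate, which is not averaged. SAP 17.3 sets none for vital signs.
- *That a bradycardia signal would be hidden.* ECG incidences, Holter interpretation, targeted medical events, events leading to interruption or discontinuation, and the vital-sign listing all remain.

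The missing incidence summary is a separate gap. It holds however SAP 9.6 is read.

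**Conclusion.** The point holds as a safety-reporting correction. Taken literally, SAP 9.6 and 17.3 turn the Day 1 vital-sign series into one Visit 2 value that retains about 20% to 50% of a fall caught at 1 h and wholly, partly or not at all at 2 h. With the Phase 1 40 mg figure that is -4.2 to -8.5 bpm over five readings, or -5.3 to -10.6 bpm over four, in place of -21.2 bpm. This is an illustration, not a forecast for a 3 mg first dose. It rests on full recovery by 4 h and on reading *time points* as visits. OLE Day 1 is affected in the same way if the rule is applied there; SAP Table 3 gives windows for the Induction period only.

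The loss is confined to the vital-sign summary. The ECG table is a partial backstop because it does not identify the Day 1 trace that counts. In addition, the vital-sign abnormality incidence called for by Protocol 9.4.3 and SAP 7.3 is absent from SAP 17.3. Efficacy inference and real-time participant monitoring are untouched.

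**What to change.** Before treatment is unblinded for the Induction Period Analysis:

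1. In SAP 9.6, limit same-day averaging to replicate readings at one nominal time.
2. In SAP 17.3 and 17.5.1, summarize Day 1 and OLE Day 1 vital signs and ECG by nominal time (predose, 1, 2, 4 and 6 h), with change from the predose value. Reconcile the baseline wording of SAP 9.5 and 9.6, including the Day 1 overlap in Table 3.
3. Add per-participant worst-postdose rows: minimum heart rate, and the heart-rate, PR and AV-block categories already in SAP 17.5.1.
4. Add the promised incidence table for abnormal vital signs, for example by applying the SAP's existing heart-rate cut-offs to pulse.

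If the Mock TFLs already show hourly rows, the SAP text should say so. The cost is SAP wording and a few table rows from data already collected.

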9.7 Statistical Tests

The default statistical significance level will be 0.05 for two-sided hypothesis tests; one-sided hypothesis tests will not be performed unless explicitly stated otherwise. The default for confidence intervals (CIs) will be to generate two-sided 95% CIs.

9.8 Common Calculations

For quantitative measurements:

- Change from Baseline = Test Value at Visit X – Baseline Value
- Percent change from Baseline = (Test Value at Visit X – Baseline Value) / Baseline Value × 100
- Proportion at Visit X = Number of participants satisfying criteria at Visit X / Total number of participants at Visit X

9.9 Statistical Software and CDISC Implementation

All analyses will be performed and data appendices will be created using SAS® software (version 9.4 or higher; SAS Institute Inc.; Cary, NC, USA). Analysis Datasets produced for analysis will follow CDISC ADaM standard IG 1.3. ADaM specifications will follow conformance rules for Define.xml v.2.0. CDISC compliance of datasets will be validated using Pinnacle 21® Enterprise software (Certara; Blue Bell, PA, USA) and Pinnacle reports will be produced.

9.10 Study Information

A general table with summary of study information will be generated, including the date of first participant signed informed consent form (ICF), and the last participant visit date and the database lock date for each unique database lock.

10. STATISTICAL CONSIDERATIONS

10.1 Missing Data

The following rules will be applied for AEs, prior medications, and concomitant medications with incomplete start dates:

- If day is missing for start date and month and year are the same as month and year for the first treatment date, then start date is set to the treatment start date.
- If day is missing for start date and month and year are not the same as month and year for the first treatment date, then impute Day 1 of the month.
- If day and month are missing for start date and the year is the same as the year for the first treatment date, then start date is set to the first treatment date.
- If day and month are missing for start date and the year is less than year for the first treatment date, then impute July 15th of the year.
- If day and month are missing for start date and the year is greater than year for the first treatment date, then impute January 1st of the year.
- If the imputed start date is greater than or equal to the corresponding non-missing end date, then start date equals the end date.

The following rules will be applied for AEs, prior medications and concomitant medications with incomplete end dates:

- If day is missing for end date and month and year are non-missing, then day will be imputed as last day of the month.
- If day and month are missing for end date and year is non-missing, then day and month will be imputed as December 31st.

The completely missing AEs and CMs start and end dates will not be imputed.

The handling of missing efficacy data is discussed in [Section 16](#).

10.2 Randomization Stratification

For the Induction Treatment Period, all participants are randomized to study treatment using permuted block randomization with block sizes of six, as specified in the Randomization

Specification Form (28 July 2021). This will be done via a IWRS. Under version 1.0 of the Protocol, the stratification factors were the following:

- biologic/JAK inhibitor *failed* status (yes/no)
- baseline corticosteroid use (yes/no)
- baseline disease activity (MMS 4-6 or 7-9)

Under subsequent Protocol versions the stratification factors are the following:

- biologic/JAK inhibitor prior use status (yes/no)
- baseline corticosteroid use (yes/no)
- baseline disease activity (MMS 5-6 or 7-9)

The randomization list was not updated to reflect these changes, and the IWRS system was kept as-is (Randomization Plan, version 2.0; 25 July 2022). For most statistical analysis purposes the following will be used:

- biologic/JAK inhibitor prior use status (yes/no)
- baseline corticosteroid use (yes/no)
- baseline disease activity (MMS 5-6 or 7-9) (i.e., participants with MMS of 4 at baseline according to IWRS are excluded from most efficacy analyses; however, see [Sections 10.5](#) and [16.1.5](#) for several analyses that include them)

In all cases, randomized stratum will be used in the primary analysis of primary and key secondary efficacy analyses. A sensitivity analysis of the primary analysis of the primary endpoint will be generated using actual stratum as collected in EDC. Descriptive statistics based on actual stratum will be generated. See [Section 16.1.7](#).

Data will be pooled across geographic region, country, and investigational site. No adjustment for these factors will be included in any statistical analysis.

